6.3 Power for Secondary Outcomes

Power for all fall injuries and all falls (regardless of injury) was calculated using the same assumptions as above, but with a 1% Type I error to control for multiplicity and no adjustment for interim analysis. Annual rates of first fall and first fall injury from MOBILIZE Boston are 0.92 (95%CI: 0.75, 1.10) and 0.57 (95%CI: 0.46, 0.69), respectively. Using conservative rates of 0.70 and 0.40, and based on the targeted sample size of 6000, power is > 99% to detect a 20% reduction with intervention relative to control for both of these secondary outcomes. For the indicators of well-being, an unadjusted sample size of 524 participants is required to detect a standardized effect size of 0.3 between intervention and control at 1 and 2 years with 80% power and 1% type I error. The sample size adjusted for missing outcomes due to death (10%/year) and lost to follow-up (5%/year with or without a serious fall injury), and for clustering (DE = 6% assuming ICC = 0.0076 with 86 practices each enrolling 8 participants) is 720 (360 per group), a 12% subsample of the 6000 participants to be accrued during year 1 of the trial.

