8.4.2 Indicators of Well-Being

Indicators of well-being include fall efficacy (measured by FES), physical function (measured by LL-FDI), anxiety and depressive symptoms (measured by Promise scales for anxiety and depression) and were measured at 12 and 24 months in a random subsample of 714 participants. Each outcome will be analyzed separately as described below.

Analysis	Indicators of well-being
Analysis population	Random subsample of 714 participants
Endpoint	Scale values at 12 and 24 months of follow-up
Unit of analysis	Participant
Method of analysis	Linear mixed model assuming missing at random (MAR)
Handling of missing data	MAR assumption
Adjustment covariates	Baseline indicator of well-being; Factors predictive of missingness: these will be determined at the time of analysis
Type I error	1% (2-sided)
Treatment effect estimate	Marginal least square mean (LSM) with 99% confidence limits if there is no treatment by time interaction ($p < 0.10$); otherwise, LSM will be summarized for each treatment and timepoint

Sensitivity analyses will be conducted to investigate the MAR assumption, such as methods that model jointly the missingness and outcome distributions (National Research Council, 2010).

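### Section 6.3 claims 80% power for the well-being indicators at both 1 and 2 years, but on its own inputs 720 participants give about 85% at 12 months and only 75–78% at 24 months

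*SAP*

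**What the plan says.** Section 6.3 (Power for Secondary Outcomes) gives the starting number for the well-being indicators: an "unadjusted sample size of 524 participants is required to detect a standardized effect size of 0.3", the difference being that "between intervention and control at 1 and 2 years with 80% power and 1% type I error". Section 8.4 makes the 1% level two-sided.

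The number is then raised to 720 (360 per group). Two adjustments are named: "The sample size adjusted for missing outcomes due to death (10%/year) and lost to follow-up (5%/year with or without a serious fall injury", and clustering, given as "DE = 6% assuming ICC = 0.0076 with 86 practices each enrolling 8 participants". The section does not print the inflation formula, does not say how the yearly rates accumulate over two years, and gives no correlation between visits or with baseline.

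Section 8.4.2 plans a linear mixed model adjusted for the baseline value in a "random subsample of 714 participants". The default treatment effect is the "Marginal least square mean (LSM) with 99% confidence limits if there is no treatment by time interaction"; "otherwise, LSM will be summarized for each treatment and timepoint".

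**The concern.** The power claim names two timepoints, but attrition accumulates, so one enrolled number cannot give the same power at both. If 720 was meant to secure 80% at the later visit, it has to absorb two years of death and loss. It appears to absorb less than that.

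The stake is how a 24-month result is read. If there is an interaction, section 8.4.2 reports the means by visit. Someone interpreting a null 24-month difference would turn to section 6.3 and credit it with 80% power, which that section's own inputs do not support. Section 6.3 also does not say whether the 80% belongs to a single-visit comparison or to the marginal effect that 8.4.2 estimates by default.

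**Working it through.** **Inputs.** From section 6.3: effect 0.3 SD, alpha 1%, equal groups, death 10%/year, loss 5%/year, design effect (DE) 1.06, enrolled 720. From section 8.4: two-sided. From section 8.4.2: actual subsample 714.

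**1. Reproduce 524.** A two-sample t-test (noncentral t) with d = 0.3 and two-sided alpha 0.01 has 79.96% power with 522 participants and 80.1% with 524. So 524 is the answer for an unadjusted comparison at a single visit. It takes no credit for baseline adjustment or repeated measures.

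**2. What 720 allows for.** 524 × 1.06 / 720 = 0.771, so 720 keeps 524 effective participants only if at least 77.1% are assessed (22.9% missing).

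**3. Retention from the stated rates.** The SAP does not say how the rates combine, so four readings are taken:

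| Reading | 12 months | 24 months |
|---|---|---|
| Rates as hazards | exp(−0.15) = 0.861 | exp(−0.30) = 0.741 |
| Death and loss compounded | 0.90 × 0.95 = 0.855 | 0.9² × 0.95² = 0.731 |
| 15%/year compounded | 0.85 | 0.85² = 0.7225 |
| Additive | 0.85 | 0.70 |

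The 0.771 that 720 can tolerate lies between the 12-month and 24-month values on every reading.

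**4. Enrolment needed and power obtained.** Needed N = 524 × 1.06 / retention. Power comes from the noncentral t with effective N = enrolled × retention / 1.06.

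| Visit, retention | N needed | Power, 720 | Power, 714 |
|---|---|---|---|
| 12 m, 0.861 | 645 | 85.1% | 84.7% |
| 12 m, 0.855 | 650 | 84.8% | 84.5% |
| 12 m, 0.85 | 653 | 84.6% | 84.2% |
| 24 m, 0.741 | 750 | 78.2% | 77.7% |
| 24 m, 0.731 | 760 | 77.5% | 77.1% |
| 24 m, 0.7225 | 769 | 76.9% | 76.5% |
| 24 m, 0.70 | 793 | 75.3% | 74.9% |

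**5. Sensitivity to the design effect.** The stated ICC and cluster size give 1 + 7 × 0.0076 = 1.053 rather than 1.06; with that value, 720 gives 75.6–78.5% at 24 months. Recomputing the design effect on the cluster size still present at 24 months (1.035–1.037) gives 76.5–79.2%, with 734–775 needed. The most lenient combination, hazards with the reduced design effect, therefore stops at 79.2%.

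**6. Where 720 might come from.** Two routes land close: 524 × 1.06 × 1.30 = 722, and 524 × 1.06 / 0.775 = 717, where 0.775 is the mean of 0.85 and 0.70. The first multiplies by 1 + d where division by 1 − d is needed. The second averages over the visits. Neither secures 80% at 24 months, and without a printed formula the cause cannot be settled.

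**7. The analysis actually planned.** The SAP gives no correlations, so those below are assumptions. With 714 participants, retention 0.85 then 0.70, monotone dropout, DE 1.06 and a normal approximation:

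| Assumed 12/24-month correlation | Marginal mean over both visits, no baseline adjustment | 24-month contrast, no baseline adjustment | 24-month contrast, baseline correlation 0.3 |
|---|---|---|---|
| 0.3 | 95.7% | 76.0% | 80.4% |
| 0.5 | 92.8% | 77.5% | 81.6% |
| 0.7 | 89.5% | 79.7% | 83.7% |
| 0.9 | 86.1% | 82.7% | 86.6% |

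**The case against.** The best defence is that the shortfall belongs to a test the SAP does not plan. Section 8.4.2 uses a baseline-adjusted mixed model, and its default effect is well above 80% under any of the correlations tried. Even the 24-month contrast recovers 80% with an assumed baseline correlation of about 0.3. This stands as a limit on the consequence. It does not rescue the printed claim, because 524 was derived without such credit and section 6.3 states no correlation to lean on.

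A second point is that the two timepoints are named in the sentence about 524, which is right at either visit, while the sentence about 720 names no visit. If 720 was based on mean retention of 0.775, it gives 80.4% at that average. This is a fair reading of an under-specified passage, but an average over visits still leaves year 2 below 80%, and a reader will carry the two timepoints over to 720.

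Third, the gap is small: under one percentage point on the most lenient reading and about five on the harshest. Under interaction, 8.4.2 speaks of summarizing means by visit and names no separate 24-month test. Recruitment has also closed, so no decision on sample size hangs on this. All of that is true and is why the point is minor. It is also true that applying design-stage attrition to the achieved 714 mixes plan and outcome, so any restated figure should say that it does so.

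**Conclusion.** The concern holds. On the inputs printed in section 6.3, 720 participants deliver the stated 80% at 12 months (84.6–85.1%) but not at 24 months (75.3–78.2% at the stated design effect, at most 79.2% on the most lenient reading). Against the 750–793 required at 24 months, 720 is 4–9% short; on the most lenient reading (734) it is about 2% short.

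This rests on an unadjusted comparison of those assessed, which is the basis that reproduces 524, and on the stated yearly rates running for two years. The practical weight is minor: the default marginal effect in 8.4.2 is adequately powered under the assumed correlations, and the shortfall bears only on the 24-month contrast. The power statement should still be corrected, because it is wrong for one of the two timepoints it names.

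**What to change.** In section 6.3, print the formula that leads from 524 to 720, including how the yearly rates accumulate, and name the contrast to which the power refers. Then restate the power by visit, for example:

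> With 714 participants and the design-stage attrition and design effect, power for an unadjusted comparison of those assessed is about 84–85% at 12 months and 75–78% at 24 months. The planned baseline-adjusted mixed model, with its marginal effect over both visits, is expected to have higher power, computed under an assumed 12/24-month correlation of [state value] and an assumed baseline correlation of [state value].

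The two values are for the trial statisticians to supply and label as assumptions. If they prefer not to assume any, the first sentence and the formula suffice.

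The cost is two sentences and one formula. No extra enrolment is proposed, and no change to data collection, analysis, alpha or estimand.

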6.4 Power for Tertiary Outcomes

There were no data to inform power calculations for the two tertiary outcomes, hospitalizations and long-term nursing home admissions.

STRIDE SAP

7. INTERIM MONITORING PLAN

7.1 Overview

Interim monitoring will focus on patient accrual, baseline comparability of treatment groups, protocol adherence, loss to follow-up, data completeness and quality, sample size assumptions, accrual of fall events, safety, efficacy, and futility. The summary of the types of tables, listings and figures (TLFs) generated for semi-annual open and closed DSMB reports is presented in the Appendix A. The final Interim Monitoring Plan (dated May 17, 2017) is given in Appendix B and was approved by the DSMB at its May 31, 2017 meeting.

7.2 Trial Adaptation Guidelines

Adaptive design features proposed in the protocol include: 1) monitoring the accrual rate to determine whether the study eligibility criteria need to be reconsidered if recruitment is lower than expected, taking into account that any changes could affect the inferences; 2) monitoring the potential for ascertainment bias because of interactions between the FCMs and study participants and changing the primary outcome definition if necessary; 3) monitoring the primary outcome rate to determine whether the outcome needs to be adapted, e.g., from time to first serious fall-related injury to time to all recurrent serious fall-related injuries if the former rate is too low, affecting the power of the study; 4) interim monitoring for efficacy or futility, if necessary; and 5) refining the analytic methods based on the validity of the assumptions; such an adaptation will be done blinded to treatment, e.g., if the death rate is low, competing risks could be considered as a secondary, rather than a primary, analysis.

Any adaptations will be presented to the DSMB for their review and approval prior to implementation. The DCC will designate an independent (unblinded) statistician for reporting to the DSMB in closed session. The independent statistician will not be involved in any operational issues in the trial once it is initiated. Only the independent statistician, along with the statistical programmer, will have access to the link between coded (A vs. B) and actual treatment assignment (intervention vs. control). All other DCC and trial personnel will remain blinded to the actual treatment assignment.

Any adaptation of eligibility criteria because of inadequate recruitment will be based on analyses of aggregate baseline screening data to determine the reasons for study ineligibility. Since these data are obtained at baseline and prior to the initiation of treatment, the analyses can be considered to be unbiased. It is expected that the study leadership will be involved in this type of adaptation.

Adaptation based on a lower than expected primary outcome rate will be done using aggregate data and presented to the DSMB in closed session by the independent statistician. No other DCC or trial personnel will be privy to these data because knowledge of the outcome rate could affect any operational decisions for the trial.

Any interim analyses for efficacy and futility will be presented in closed session to the DSMB by the independent statistician. Treatments will be designated as A vs. B. The independent statistician will have access to the actual treatment assignment during the closed session, if requested by the DSMB. No one else associated with the trial will be privy to these data.

STRIDE SAP

Refining the Statistical Analysis (SAP) plan will be done blinded to treatment by the DCC blinded trial statisticians. If the outcome is changed the DCC statisticians will need to be aware of the change, in addition to the independent statistician, in order to be able to appropriately revise the SAP.

7.3 Monitoring Inter-Practice Variation

Because of the concern raised by the DSMB at its initial meeting about inter-practice variation and its potential effect on the power of the trial, we monitored the effect of clustering using a variance inflation factor (VIF) approach. That is, the inflation in variance for the treatment effect for the model with clustering vs. the model without clustering. This approach was used because of the complexity of the analytic model, a clustered survival model with competing risk due to death, and the lack of a closed form ICC for this model. The VIF was determined by the unblinded trial statisticians and presented in the closed DSMB session.

7.4 Monitoring of Efficacy and Futility

Per RFA, a “preliminary statistical analysis of the effects of the preventive strategy on the rate of serious fall injuries must be reported in March 2017.” At this time, recruitment will have ended and about 55% of the expected number of primary events will have been accrued, sufficient for an interim look. The expected number of events is based on the ratio of average follow-up time at the interim look (1.25 years) relative to the average total follow-up time for the study (2.25 years), assuming recruitment begins on June 1, 2015. Thus, we propose consideration of stopping the trial at this time only for compelling evidence of efficacy ($\sim p < 0.008$) or a trend in the wrong direction (i.e., futility) taking into account trends in secondary outcomes. Future looks will be left to the purview of the DSMB based on emerging trends in the data; however, by March 2017, there will be less than one year left in the trial and it may be impractical to conduct another interim look before it ends in February 2018. Interim monitoring boundaries will be established using an alpha spending approach using EAST version 6.13 (Cytel) software (Jennison and Turnbull, 2000; Proschan, Lan and Wittes, 2006). A prototype figure is given in the Appendix.

In addition to formal sequential monitoring boundaries, estimates of conditional power will be provided to assess the likelihood of reaching a significant conclusion at the end of the trial given the observed data (Lan and Wittes, 1988).

On December 13, 2017, a protocol amendment was approved changing the interim monitoring (with DSMB approval) from efficacy and futility to efficacy or futility, if necessary.

7.5 Monitoring of Safety

Details of the safety and adverse event monitoring plan were provided in the study protocol. Because STRIDE is a low risk trial and an experimental intervention is not being used, only serious adverse events related to hospitalization and death will be collected. Adverse events will not be collected. The vast majority of SAE ascertainment will occur from postal questionnaire and telephone follow-up and/or in aggregate via biannual data downloads from the EHR and claims data. Unanticipated problems will also be reported directly to the Medical Safety Monitor from the sites.

STRIDE SAP

The distribution of hospitalizations, deaths and types of unanticipated problems will be summarized overall and by treatment. Death rates will be calculated by the method of Kaplan-Meier. A listing of the safety tables and figures to be presented to the DSMB are summarized in the Appendix.

8 ANALYTIC PLAN

8.1 Overview

The analysis of the primary and secondary outcomes will be according to the principle of intent-to-treat, i.e., practices/participants will be analyzed according to their original treatment assignment regardless of adherence to protocol. All analyses will account for the cluster design with the participant as the unit of analysis. SAS 9.4 and R 3.6.1 software will be used for all analyses.

8.2 Comparability of Treatment Groups

Comparability of treatment groups will be assessed by comparing the distribution of baseline characteristics in the two groups using appropriate graphical procedures, summary statistics and multivariate methods. The randomization is designed to produce balance on important covariates at the practice level (unit of randomization) but not necessarily at the patient level. Therefore, in a secondary analysis, the following pre-specified set of baseline covariates will be selected for adjustment to determine their influence on the treatment comparisons: age, race/ethnicity, education, number of chronic conditions, and number of positive screening items (out of three) for serious fall injuries (Senn, 1989).

Note: Sections 8.3 – 8.5 were revised to provide more analytic detail than presented in version 1.0 of the SAP, including more recent statistical advances. The revised plan is consistent with the original analytic plan. The trial protocol has been revised accordingly.

8.3 Analysis of Primary Outcome: Adjudicated Serious Fall Injury

8.3.1 Primary Analysis of Primary Outcome: Adjudicated Confirmed First Event

Analysis	Primary analysis of primary outcome: adjudicated confirmed first serious fall injury
Analysis population	All enrolled participants
Endpoint	Time to first adjudicated confirmed serious fall injury
Unit of analysis	Participant
Method of analysis*	Multistate survival model that incorporates competing risks due to death and clustering (Putter et al., 2007; Lee et al., 1992; R

STRIDE SAP

	Package 'survival': https://cran.r-project.org/web/packages/survival/survival.pdf)
Calculation of follow-up time	Time from date of enrollment to the earliest of: date of first confirmed serious fall injury, date of last completed patient or proxy interview, or date of death.
Adjustment covariates	Cluster-level covariates: healthcare system; constrained-covariate randomization balancing factors: practice size (tertiles), geography (urban vs. rural), and race/ethnicity (majority primary identification: nonwhite vs. white)
Type I error	5% (2-sided)
Control of type I error	None
Treatment effect estimate	Hazard ratio with 95% confidence limits

* If the multistate model does not converge, we will fit the Zhou et al. (2011) model. In the event there are practices with no events that create convergence issues with fitting patient-level models for the primary outcome [i.e., multistate and Zhou et al. (2011)], the primary analysis will default to a practice-level analysis as described below.

Sensitivity analysis: Adjustment for pre-specified set of patient-level covariates (in addition to cluster-level covariates): age, sex, race/ethnicity, education, number of chronic conditions, and number of positive screening items for serious fall injuries.

Subgroup analysis: The effect of intervention will be evaluated in the following prespecified subgroups of participants using appropriate tests of homogeneity (e.g., interaction): age (70-79, 80+), sex (male, female), fear of falling alone (yes, no), multimorbidity (0-1 chronic conditions, 2+ chronic conditions), and hip fracture or other fracture since age 50 (yes/no)]. The Hochberg (1988) procedure will be used to control for multiplicity for the tests of interaction using an overall type I error of 5% (2-sided).

Cumulative incidence rates: The cumulative incidence of first serious fall injury will be estimated using non-parametric maximum likelihood methods (Aalen-Johansen estimator; Putter et al, 2006) and will be used to estimate freedom from falling over the entire follow-up period.

Supplementary Practice-level analysis: This analysis will be based on a Poisson regression model using total practice-level follow-up time as an offset, adjusted for healthcare system and the cluster-level covariates [healthcare system; constrained-covariate randomization balancing factors: practice size (tertiles), geography (urban vs. rural), and race/ethnicity (primary identification: nonwhite vs. white)]. [We note that the practice-level analysis is a planned supplementary analysis and will default to the primary analysis only if the multistate and Zhou models do not converge.]

STRIDE SAP

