Primary Analysis	The risk of any serious fall injury (i.e., time to first event) will be analyzed using a survival model that incorporates competing risks (due to death) and clustering. In this analysis, participants who are lost to follow-up without a prior serious fall-related injury will be censored at their date last seen. In a secondary analysis, we will adjust for the pre-specified set of baseline covariates to examine their influence on the intervention effect.

STRIDE SAP

Secondary Outcomes	Number of falls, number of all fall injuries, and measures of well-being.
Adaptive Components	Adaptive components of the trial include: 1) monitoring the accrual rate to determine whether the study eligibility criteria need to be reconsidered if recruitment is lower than expected, taking into account that any changes could affect the inferences; 2) monitoring the potential for ascertainment bias because of interactions between the FCMs and study participants and changing the primary outcome definition if necessary; 3) monitoring the primary outcome rate to determine whether the outcome needs to be adapted, e.g., from time to first serious fall-related injury to time to all recurrent serious fall-related injuries if the former rate is too low, affecting the power of the study; 4) interim monitoring for efficacy or futility, if necessary; and 5) refining the analytic methods based on the validity of the assumptions; such an adaptation will be done blinded to treatment, e.g., if the death rate is low, competing risks could be considered as a secondary, rather than a primary, analysis.
Interim Analysis	Interim monitoring will focus on patient accrual, baseline comparability of treatment groups, protocol adherence, data completeness and quality, accrual of fall events, safety, and efficacy or futility.

STRIDE SAP

PROTOCOL VERSION HISTORY (revised 7/31/2018)

Version	Date	Changes
2.7	7/31/2018	1. Extend the study from a minimum of 20 and maximum of 40 months follow-up to a minimum of 24 and maximum of 44 months of follow-up. Final end date of the study, including the analytic phase is now extended to April 30, 2020.
2.6	6/1/2018	1. The definition of the primary outcome has been modified to reflect the recommendations of the Ad Hoc Expert Panel established by the NIA and NIA's concurrence with this recommendation.

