8.3.2 Supportive Analysis of the Primary Outcome: Adjudicated Confirmed Recurrent Events

Analysis	Supportive analysis of primary outcome: all adjudicated confirmed serious fall injuries (recurrent events)
Analysis population	All enrolled participants
Endpoint	Times to recurrent adjudicated confirmed serious fall injuries
Unit of analysis	Participant
Method of analysis*	Joint frailty model with recurrent events and death as a semi-competing risk (Jung et al., 2018).
Calculation of follow-up time	Time from date of enrollment to the earlier of date of the last completed patient or proxy interview, or date of death.
Adjustment covariates	Cluster-level covariates: healthcare system; constrained-covariate randomization cluster-level balancing factors: practice size (tertiles), geography (urban vs. rural), and race/ethnicity (majority primary identification: nonwhite vs. white)
Type I error	5% (2-sided)
Control of type I error	None
Treatment effect estimate	Hazard ratio with 95% confidence limits

*If the Jung model does not converge, we will fit a practice-level analysis as described above.

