8.5 Analysis of Tertiary Outcomes

Hospitalizations will be analyzed using a Poisson regression model accounting for practice-level clustering with follow-up time as an offset. Time to first long-term nursing home admission will be analyzed using the multistate model accounting for clustering (as described for primary outcome). Death will be analyzed using the marginal Cox model (Lee et al, 1992). No control for multiplicity will be done for these analyses.

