The primary outcome is first adjudicated SFI. Because adjudication of outcomes will lag behind the accrual of patient reported SFI, an estimate of the conversion rate (with 95% confidence intervals) will be calculated from the accumulated data, i.e., proportion of reported events in which adjudication has been completed (i.e., resolved) that meet the definition of a primary study outcome. Separate conversion rates may need to be estimated for the different types of SFI (Types 1 and 2). The conversion rate will be used to estimate the projected number of adjudicated first SFI at the end of the 40-month trial based on the observed patient reported first SFI rate and the projected total person years of follow-up (PYF) accounting for censoring due to deaths and losses. The observed patient reported first SFI event rate will be estimated as the number of observed patient-reported first SFI divided by the observed total PYF. The projected adjudicated events will then be estimated as:

Projected adjudicated SFI = observed first patient reported SFI rate x projected total PYF x adjudication conversion rate.

A comparison of the projected number of adjudicated events with the target number of control events (723), after accounting for the estimated ICC, for 90% power (or, if necessary, 540 events for 80% power) will be used to assess whether an extension of follow-up is needed and for how long a duration (see 2c below).

As a supportive strategy, we will also calculate the control event rate. A control event rate of 0.14/year was assumed in the sample size calculations for 90% power; a rate of approximately 0.10/year is needed for 80% power. The sample size calculations also assumed a 7% annual death rate (competing risk) and 3% annual loss to follow-up (censoring) rate. We propose a cumulative incidence rate calculation (with 95% confidence intervals) that considers the censoring and competing risk rate, instead of the Kaplan Meier rate which counts losses and deaths as independent censoring. If the lower bound for the observed rate is greater than the hypothesized control rate of 0.14 for 90% power or 0.10 for 80%, then there is some assurance that the study is on target for 80%/90% power to detect the hypothesized effect, a hazard ratio of 0.80.

2c. Extending Follow-up or Adapting the Primary Outcome from First SFI to All SFI to Maintain Study Power

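### Read literally, the follow-up rule in SAP 8.3.1 and 8.3.2 leaves out every known death that is not followed by a proxy interview, although both models need those deaths as events

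*SAP*

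**What the plan says.** In section 8.3.1 (primary analysis, first event), the row for calculating follow-up time runs from enrollment to "the earliest of: date of first confirmed serious fall injury, date of last completed patient or proxy interview, or date of death". The model in that table is a multistate survival model with death as a competing risk. If it does not converge, the fallback is a competing-risks regression for clustered data. The cumulative incidence, an Aalen-Johansen estimate, "will be used to estimate freedom from falling over the entire follow-up period".

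In section 8.3.2 (recurrent events), the same row reads "Time from date of enrollment to the earlier of date of the last completed patient or proxy interview, or date of death". The model is a "Joint frailty model with recurrent events and death as a semi-competing risk".

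Three other places show how deaths were meant to be treated:
- Study Summary, Primary Analysis row: the model incorporates death as a competing risk, and "participants who are lost to follow-up without a prior serious fall-related injury will be censored at their date last seen". No such rule is given for deaths.
- Section 8.5: "Death will be analyzed using the marginal Cox model". Dates of death are therefore in the analysis data.
- Appendix B, Stage 2b: the interim control rate is to be a cumulative incidence, "instead of the Kaplan Meier rate which counts losses and deaths as independent censoring".

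**The concern.** The two rows take a minimum over the last interview and death. For someone who dies, the last interview almost always comes first, so naming death in the row does not make it count. A programmer who follows the row censors that participant at the last interview. The death then never enters the competing-risks data, and any confirmed injury dated between that interview and the death is dropped too.

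To the extent this happens:
- the Aalen-Johansen curve drifts toward 1 minus Kaplan-Meier, so cumulative incidence and the absolute difference between arms are overstated and freedom from injury is understated;
- the joint frailty model loses that share of its death component;
- the competing-risks fallback sees fewer competing events.

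Another programmer might code death at the interview date, which mistimes it, and a third might use the date of death. A final SAP should not leave that open.

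**Working it through.** **1. Logic of the rule.** Let L be the date of the last completed interview, D the date of death and F the date of first confirmed injury. Unless a proxy interview is completed on or after D, L < D. Then min(F, L, D) ≤ L < D, so follow-up ends at F or at L and never at D. The same holds for min(L, D) in 8.3.2. Death is reached only through a later proxy interview. Call the share of deaths with one q. The SAP does not give q, so it is varied from 0 to 1.

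**2. Inputs.** Control injury rate 0.14 a year, hazard ratio 0.80, death 7% a year and loss 3% a year (section 6.2). Death below 2% in both source studies (section 6.1), taken here as 2%. Lower benchmark rate: "a rate of approximately 0.10/year is needed for 80% power" (Appendix B, Stage 2b). Interviews every 4 months (section 4, Table 1). Follow-up 24 to 44 months (Protocol Version History, 2.7), mean (24 + 44)/2 = 34 months under uniform accrual. 5,451 enrolled. Assumed: constant hazards, injury independent of death, and a closing interview for survivors.

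**3. The plan's own figures.** Events = 4(1.960 + 1.282)²/(ln 0.80)² = 844.1, rounded up to 845, as in section 6.2. With s = l + d + c (injury, death and loss hazards), accrual R and duration T, the event probability is (l/s)·[1 − (e^(−s(T−R)) − e^(−sT))/(sR)]. For R = 1.5 and T = 3 this gives 0.2416 (control) and 0.1990 (intervention), mean 0.2203. Then 844/0.2203 × 1.03 × 1.53 ≈ 6,038, against 6,030 in Table 2. The design calculation therefore does treat death as a competing event.

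**4. Cumulative incidence.** With death hazard d = (annual death rate) × q, incidence at t is l/(l + d)·(1 − e^(−(l + d)t)), or 1 − e^(−lt) when d = 0. At t = 34/12 years and 7% deaths:

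| Control rate | Deaths kept | d | Control | Intervention | Difference (points) |
|---|---|---|---|---|---|
| 0.14 | all | 0.07 | 29.9% | 24.8% | 5.1 |
| 0.14 | 90% | 0.063 | 30.2% | 25.0% | 5.1 |
| 0.14 | half | 0.035 | 31.3% | 26.0% | 5.3 |
| 0.14 | none | 0 | 32.7% | 27.2% | 5.6 |
| 0.10 | all | 0.07 | 22.5% | 18.5% | 4.0 |
| 0.10 | half | 0.035 | 23.5% | 19.3% | 4.2 |
| 0.10 | none | 0 | 24.7% | 20.3% | 4.4 |

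At 2% deaths, control incidence is 31.9% with all deaths kept and 32.7% with none (rate 0.14), or 24.0% and 24.7% (rate 0.10). At 44 months with 0.14 and 7%, it is 35.8% (all), 37.9% (half) and 40.2% (none).

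**5. Events in the data.** Simulation with 4-monthly interviews, scaled to 5,451 participants, control rate 0.14:

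| Annual deaths | Rule | Injuries | Competing deaths |
|---|---|---|---|
| 7% | death counted at its date | 1,418 | 793 |
| 7% | literal, half kept | 1,410 | 397 |
| 7% | literal, none kept | 1,402 | 0 |
| 2% | death counted at its date | 1,515 | 241 |
| 2% | literal, none kept | 1,510 | 0 |

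At 7% deaths, the dropped injuries number about 8 to 17 before rounding, or 0.6% to 1.2% of 1,418.

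**6. Treatment effect and power.** The simulated cause-specific hazard ratio stays within 0.004 of 0.80 under every rule. Power = Φ(√(events/1.524/4) × 0.2231 − 1.96), where 1.524 = 1 + 69 × 0.0076. This gives about 92.5% for 1,418 events and 92.3% for 1,402. The approximate subdistribution ratio at 34 months, ln(1 − incidence, intervention)/ln(1 − incidence, control), is 0.802 with all deaths kept and 0.800 with none.

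**The case against.** The best defence is that this is a wording slip and the intent is plain. Both tables name death as an event and list its date, the Study Summary and Appendix B point the same way, and an analyst who fitted a competing-risks model with few or no competing events would notice. Proxy interviews are expressly allowed. Section 7.5 expects most deaths and hospitalizations to be learned through questionnaire and telephone contact or record downloads, so some deaths would have a later contact. The extreme with no deaths kept is therefore unlikely, and the 7% death rate was deliberately set above the source data. With 90% of deaths kept, control incidence moves only from 29.9% to 30.2%. It can also be said that the Study Summary is silent on the timing of deaths rather than in conflict with the row, and that extending time beyond the last interview only for people known to have died makes follow-up depend on outcome.

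Much of this stands as a limit on size. The intent is conceded, the share is unknown, and the primary test is safe. It does not rescue the rule. Clear intent does not change what a minimum computes, and nothing in the SAP says that a proxy interview follows every death. Section 7.5 does not show that a completed interview follows. The outcome-dependence worry is small: when deaths are counted at their own date, the simulated death hazard is 0.0703 against a true 0.07, and the injury hazards are recovered at 0.140 and 0.112.

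**Conclusion.** The concern holds: the rows are wrong as written and should be fixed. They are stated rules, not omissions, and they contradict the models they feed. The damage falls on the cumulative incidence and the absolute difference, the death component of the joint frailty model, and the count of competing events available to the fallback. At the design rates and 34 months, the overstatement of control incidence runs from nothing, if a proxy interview follows every death, to 2.8 points (32.7 − 29.9) if none does. The difference between arms is overstated by up to about 0.5 points. At 2% deaths the overstatement of incidence is at most about 0.8 points. The primary cause-specific hazard ratio and power are essentially unchanged, provided injury and death are independent. The effect on the joint frailty treatment estimate was not quantified.

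**What to change.** Add one precedence clause to the follow-up row in both 8.3.1 and 8.3.2:
- Follow-up ends at first confirmed serious fall injury (8.3.1 only) or, for a participant not withdrawn or lost before then, at the date of a known death. Status is then death, competing in 8.3.1 and semi-competing in 8.3.2, whether or not a proxy interview follows.
- The last completed interview is the censoring date only for participants not known to have died while under follow-up.
- Participants lost or withdrawn stay censored at the date last seen, as the Study Summary says.
- Confirmed injuries dated between the last interview and such a death count as events.

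The cost is one clause in two table rows and a re-derivation of time and status from dates the SAP already uses. There is one small downside. The stretch between the last interview and death rests on claims, records or proxy reports, so injuries in it may be slightly under-ascertained in both arms. Sections 8.4.1 and 8.5 borrow the primary-outcome method and should be checked for the same clause.
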